4.2 Rationale

4.2.1 Rationale for the Trial and Selected Subject Population

This study is being conducted to assess the initial clinical safety, tolerability, PK, and PD of MK-1092 following administration to humans. PK after SC administration will be assessed. PD will be assessed by measuring the glucose infusion rate (GIR) after administration of MK-1092 under euglycemic clamp conditions. In addition, the glycemic effect of Humalog infusion following SC MK-1092 administration will be assessed, also under euglycemic clamp conditions.

The study population is comprised of healthy male and female (women of non-child bearing potential, WONCBP) subjects, adult subjects with T1DM, and adult subjects with T2DM. In Parts 1 and 2 of the study, MK-1092 will be administered to healthy subjects to gain an initial understanding of the safety/tolerability, PK, and PD profile of MK-1092 prior to administration in adult subjects with T1DM and T2DM. Because the target population for MK-1092 includes patients with T1DM and T2DM, including adult subjects with T1DM and T2DM in this protocol will provide an early read-out of the therapeutic potential for MK-1092.

Adult subjects with T1DM and T2DM will not be administered MK-1092 until a safe and tolerated dose that achieves a GIR \sim 1-2 mg/kg/min (Part 1) and that has been tested with Humalog infusion (Part 2) in healthy adult subjects is identified. At the time of protocol amendment 03, a dose of 8.0 nmol/kg has fulfilled this requirement and was tested in Part 3 Panel G. Female subjects of child-bearing potential are not included in this study due to the limited assessment of MK-1092 on reproduction and development. At the time protocol amendment 03, approximately 77 subjects will participate in the study, including up to approximately 44 healthy male and female subjects (40 in Part 1, 4 in Part 2) in the age range of 18-50 years (inclusive), up to approximately 24 male and female adult subjects with T1DM (Part 3) in the age range of 18-60 years (inclusive), and up to approximately 9 male and female adult subjects with T2DM (Part 4) in the age range of 18-60 years (inclusive).

4.2.2 Rationale for Dose Selection/Regimen/Modification

As this is a Phase I assessment of MK-1092 in humans, and the pharmacokinetic, pharmacodynamic and safety profiles of the compound are still being evaluated, modifications to the dose or dosing regimen may be required to achieve the scientific goals of the trial objectives and/or to ensure appropriate safety monitoring of the trial subjects. Details of allowed modifications are provided in Section 7.1.5.5 - Trial Design/Dosing/Procedures Modifications Permitted within Protocol Parameters.

As noted above, there are several objectives in this trial, extending beyond the standard goals of a FIH trial in understanding safety, tolerability, and PK. Specifically, the trial is designed to also examine PD of MK-1092 with respect to the short-term glycemic effect of MK-1092 across a range of doses in comparison to a single dose of glargine insulin, provide an assessment of the ability of MK-1092 to inhibit lipolysis, and test the glycemic effect of IV Humalog following SC administration of MK-1092. Subjects in Parts 1, 3, and 4 will receive MK-1092 SC or glargine to assess safety, tolerability, PK, and PD from this mode of delivery. Healthy adult subjects in Part 2 will receive MK-1092 as well as an infusion of Humalog to explore the glucose-lowering potential of Humalog infusion after SC administration of MK-1092. Initiation of Part 2 occurred after safety and tolerability of 8.0 nmol/kg dose after SC administration in Part 1 had been assessed. Adult subjects with T1DM in Part 3 and adult subjects with T2DM in Part 4 will receive MK-1092 SC or glargine to assess safety, tolerability, PK, and PD from this mode of delivery in a target patient population. The first panel of Part 3 tested MK-1092 8.0 nmol/kg SC, a dose demonstrated to be safe and tolerated in healthy subjects, that has achieved GIR \sim 1-2 mg/kg/min in Part 1, and that has been tested with Humalog infusion (Part 2) in healthy adult subjects. The first period of Part 4 will use MK-1092 32 nmol/kg, which was demonstrated to be safe and well-

tolerated in Part 1. Each subject in Part 4 will receive single dose administration in up to three different periods. This approach will allow for assessment of GIR at more than one dose level in subjects with T2DM.

4.2.2.1 Rationale for the Use of Comparator/Placebo

In Parts 1, 3, and 4, glargine insulin will be administered to confirm the PD profile of glargine compared to MK-1092 and to serve as a safety comparator in healthy adult subjects (Part 1), in adult subjects with T1DM (Part 3), and in adult subjects with T2DM (Part 4). To facilitate blinding, subjects participating in Parts 1, 3, and 4 will receive injections of MK-1092/glargine and placebo matched to the alternative active treatment. PD will be assessed as the GIR required to maintain the prespecified euglycemic clamp (~5% below fasting glucose levels for healthy adult subjects or at ~100 mg/dL for adult subjects with T1DM and T2DM). Both glargine and MK-1092 will be administered as a single SC dose. Glargine 3.0 nmol/kg (0.5 units/kg) will be used in all panels of Parts 1 and 3 and all periods of Part 4. Glargine has been chosen as a comparator as it is a commonly used basal insulin in management of T1DM and T2DM. The 3.0 nmol/kg dose achieves GIR ~2 mg/kg/min between 6 and 18 hr after SC dosing in healthy adult subjects [3] and shown to have similar effects on GIR in adult subjects with T1DM [4]. Furthermore, the 3.0 nmol/kg dose has clinical relevance as it falls within a range of glargine used by patients with diabetes. Given underlying insulin resistance in subjects with T2DM, it is anticipated that GIR_{max} following glargine 3.0 nmol/kg will be no higher in adult subjects with T2DM than healthy adult subjects and adult subjects with T1DM.

In Part 2, Humalog will be infused for 3 hr, starting ~12 hr after SC administration of MK-1092. The timing of the Humalog infusion has been chosen to correspond to a time at which MK-1092 is anticipated to have a glycemic effect, though the actual starting time of the Humalog infusion may be altered based on data from Part 1. The dose of IV Humalog (0.2 units/kg = 1.2 nmol/kg over 3 hr) is near the range of insulin used in clinical practice to treat diabetic ketoacidosis. The GIR during IV Humalog infusion after SC administration of MK-1092 was anticipated to be > 4 mg/kg/min, which is a GIR above that required for suppression of hepatic glucose production [5], and likely ~9-11 mg/kg/min, which approaches the maximal GIR observed in the literature [6].

In addition to measuring GIR as a PD endpoint, serum free fatty acids (FFA) or non-esterified fatty acids (NEFA) and plasma glycerol will also be assessed in all parts as a comparator for the lipolysis effect of MK-1092. The PK of glargine will also be assessed in Parts 1, 3 and 4.

4.2.2.2 Starting Dose for This Trial

The proposed starting dose of MK-1092 for this trial is 4.0 nmol/kg SC, which will be administered to healthy adult subjects in Part 1. This starting dose was selected in accordance with regulatory guidelines, which recommend a starting dose of 1/10th the NOAEL at the human equivalent dose (HED) in the more sensitive species, correcting for body surface area. For MK-1092, the more sensitive species for calculating the starting dose is the dog, as it is the species in which the lowest HED can be identified. The NOAEL SC

dose of 3.0 mg/kg/d (255.5 nmol/kg) supports the starting dose of 4.0 nmol/kg SC dose in humans, based on the following:

The bioavailability of MK-1092 in dogs is 0.67, which makes the 3.0 mg/kg/d SC dose roughly equivalent to 2.0 mg/kg IV, or 170 nmol/kg (molecular weight of MK-1092 is 11,751 g/mol = 11,751 mg/mmol). Multiplying 170 nmol/kg * 0.54 (correction for body surface area) = 91.8 nmol/kg * 0.1 (safety factor) = 9.18 nmol/kg. This dose is calculated using the unlikely and highly conservative assumption of 100% bioavailability from SC administration in humans and still has a ~2.3x margin to the proposed initial SC dose of 4.0 nmol/kg. Based on translational PK/PD modeling, the starting dose of 4.0 nmol/kg SC has a projected exposure of 9.1 nM*hr assuming F=0.4, which is the lowest bioavailability observed in pre-clinical species. The observed exposure of MK-1092 4.0 nmol/kg was 9.86 nM*hr, which supports the assumption of F ~ 0.4. The assumption of F=0.4 is used in subsequent calculations unless otherwise specified.

The projected effective range for MK-1092 for clinical administration in both healthy adult subjects and adult subjects with T1DM has been estimated based on preclinical studies and extensive modeling to be 12.6 nmol/kg SC. The projected effective range for MK-1092 in adult subjects with T2DM may be twice as high (~ 25 nmol/kg SC) given the presence of insulin resistance in this population. This is the dose at which the GIR in a euglycemic clamp is expected to run at ~1-2 mg/kg/min, which is a generally accepted GIR for suppression of hepatic glucose production and thus a likely target for clinical dosing. A SC dose of 12.6 nmol/kg is projected to lead to an exposure (AUC_{0-24hr} at steady state) of 29 nM*hr, assuming linear PK. A range of exposure around this predicted therapeutic dose was anticipated in Part 1 between Panels B (8.0 nmol/kg SC) and C (16 nmol/kg SC). The observed AUC_{0-24h} was 12.9 nM*h at 8.0 nmol/kg and 26.0 nM*h at 16 nmol/kg.

There were no adverse toxicities noted in pre-clinical studies. Reductions in blood glucose were observed as would be expected from the pharmacology of an insulin; thus, NOAELs for MK-1092 are derived from the top doses in both rat (20 mg/kg/d SC) and dog (3.0 mg/kg/d SC), which led to exposures of 3650 nM*hr and 479 nM*hr at 2 weeks, respectively. The exposure margin is based on the dog levels and is thus ~52x for the 4.0 nmol/kg starting dose and ~16x for the 12.6 nmol/kg SC projected therapeutic dose.

For Part 2, in which healthy adult subjects will be infused with Humalog after SC administration of MK-1092, the dose of MK-1092 that achieves the GIR_{max} of ~1-2 mg/kg/min in Part 1 will be used. Therefore, Part 2 will not start until the starting dose to be used has been explored in Part 1 (without co-administration with Humalog). The dose that achieves GIR ~1-2 mg/kg/min will be used in Part 2 because it is a dose that will suppress hepatic glucose production and nears the target GIR for MK-1092 in healthy adult subjects and in adult subjects with T1DM.

For Part 3, in which adult subjects with T1DM are receiving MK-1092 via SC injection, the first dose was 8.0 nmol/kg, as determined by data from Part 1. Specifically, the starting dose in Part 3 will be no higher than a safe and tolerated dose that achieves GIR ~1-2 mg/kg/min (Part 1) and that has been tested with Humalog infusion (Part 2) in healthy adult subjects. Dosing in Part 3 started after completion of the SC MK-1092 panel at the same or higher

dose in healthy adult subjects in Parts 1 and 2. Dosing in all subsequent panels of Part 3 will commence upon review of the safety data from previous panels within Part 3 and determination of an acceptable safety profile to continue dose escalation. The therapeutic exposure is expected to be similar in healthy adult subjects and adult subjects with T1DM.

For Part 4, in which adult subjects with T2DM are receiving MK-1092 via SC injection, the first dose will be 32 nmol/kg, which is below the highest dose tested in Part 1 as of the time of protocol amendment 03 (64 nmol/kg MK-1092), and which was safe and well-tolerated. Dosing in all subsequent periods of Part 4 will commence upon review of the safety data from previous periods and determination of an acceptable safety profile to continue dose escalation. The therapeutic exposure is expected to be higher in adult subjects with T2DM than in healthy subjects or adult subjects with T1DM given the presence of greater insulin resistance.

Up to 3 doses of MK-1092 in Part 3 and up to 3 doses of MK-1092 in Part 4 will be administered in succession in each part; however, Part 3 and Part 4 may be dosed in parallel. The highest dose of MK-1092 in Part 3 and Part 4 will not exceed 64 nmol/kg SC, which is the highest planned clinical dose. Adult subjects with T1DM and T2DM may also be randomized to glargine in Part 3 and Part 4. The 3.0 nmol/kg dose (0.5 units/kg) of glargine is anticipated to achieve GIR \sim 2 mg/kg/min based on the literature [4] and is clinically relevant as it approximates a commonly used amount of insulin for patients with diabetes.

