A summary of the observed PK for the MK-1092 4.0 nmol/kg to 64 nmol/kg dose groups in Part 1 and for Part 3 Panel G (8.0 nmol/kg) is provided below. The PK from Part 3 Panel H and from Part 4 (Periods 1 and 2) is pending at the time of amendment 04.

| Preliminary PK Parameters for MK-1092-001 Part 1 (4.0 – 64 nmol/kg) and Part 3 (8.0 nmol/kg) | | | | | | |
|---|-----------------------|---|-----------------------------|-----------------------------|----------------------------------|-------------------------------------|
| | Dose (nmol/kg) | T_{max} (hr)[¶] | t_{1/2} (hr) | C_{max} (nM) | AUC_{0-∞} (nM·hr) | AUC_{0-24hr} (nM·hr) |
| Part 1 | 4.0 | 18 (9.0-18) | 7.00 (31.42) | 0.382 (21.70) | 9.86 (15.37) | 6.43 (20.78) |
| | 8.0 | 12 (4.0-18) | 6.37 (25.85) | 0.747 (25.03) | 17.8 (15.36) | 12.94 (22.49) |
| | 16 | 18 (4.0-24) | 5.47 (27.90) | 1.63 (12.68) | 37.8 (10.09) | 26.03 (21.43) |
| | 32 | 18 (9.0-18) | 5.79 (16.91) | 2.91 (18.73) | 75.8 (10.28) | 48.86 (15.83) |
| | 64 | 12 (12-18) | 9.03 (73.0) | 6.82 (27.6) | 161 (14.1) | 108 (27.1) |
| Part 3 | 8.0 | 15 (9.0-18) | 7.81 (21.6) | 0.788 (20.4) | 22.6 (22.4) | 13.9 (17.8) |
| [¶] Median (Min-Max). All other parameters are expressed as geometric mean (CV). | | | | | | |

Exposures were comparable to predicted values. Following a single dose administration, the geometric mean of apparent terminal half-life ranged ~5.5-9 hr and T_{max} ranged ~12-18 hr at 4.0 nmol/kg to 64 nmol/kg in Part 1. MK-1092 AUC_{0-∞} and C_{max} appeared to be approximately dose proportional. The PK parameters for 8.0 nmol/kg were similar in Part 1 and Part 2 based on preliminary analysis. The PK parameters at 8.0 nmol/kg in Part 3 were comparable to the PK parameters at 8.0 nmol/kg in Part 1.

No anti-drug antibodies (ADAs) or anti-insulin antibodies (AIA) have been detected in Part 1 Panel A-D, Part 2, or Part 3 at up to 28 days after dosing. In Part 1 Panel E, no ADA or AIA have been detected at up to 28 days in 7 of 8 subjects; the 8th subject was lost to follow-up after 14 days and no ADA and AIA had been detected at up to 14 days after dosing for this subject.

Preliminary Pharmacodynamics

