4.2.2.3 Maximum Dose/Exposure for This Trial

In preclinical toxicity studies, reductions in blood glucose, which were not considered adverse, were observed in both rat and dog. Biliary duct findings, which were also not considered adverse, were observed in the dog only. As directed by the CTA Guidance [ICH Topic M3 (R2)], the maximum allowable exposure in this trial is the lower exposure (AUC) in either species at the highest dose tested, as neither species demonstrated toxicity and at least 3 dose levels were assessed in both.

The upper range for dosing in this study has been selected based on preclinical studies, emerging clinical data, and extensive modeling to provide exposure levels several fold above those projected to be needed in subsequent clinical studies. For example, the therapeutic exposure level for insulin resistant subjects with T2DM is estimated to be 58 nM*h, which is twice that for healthy adult subjects and adult subjects with T1DM. Thus, the maximum dose in this study of 64 nmol/kg is projected to lead to an exposure (AUC_{0-∞}) of 146 nM*hr, or \sim 2.5x that required for therapeutic exposure in T2DM. In the highly unlikely setting of F=1, exposure at 64 nmol/kg SC could be 366 nM*hr, a value which is provided only as a highly conservative benchmark.

As noted above, the lower NOAEL was observed in dog, in which a dose of 3.0 mg/kg/d SC led to an AUC_{0-24hr} level of 479 nM*hr on the last day of dosing. According to regulatory guidance, the maximum clinical dose should not lead to exposure levels that exceed this level. The maximum SC dose of 64 nmol/kg has a predicted exposure margin for AUC_{0-∞} of \sim 3.3x assuming F=0.4 or \sim 1.3x assuming the highly unlikely F=1. Therefore, safety margins for this maximum planned clinical dose are adequate. Further, this dose may not be

administered if PD targets have been reached at earlier doses, if there are unexpected safety findings or if a revised projected exposure based on PK obtained during this trial would not lead to a satisfactory margin. With respect to the reductions in blood glucose seen in the preclinical toxicity studies, note that subjects in this trial will be receiving a glucose infusion via the euglycemic clamp. Subjects will be intensively monitored, with frequent assessment of blood glucose, even after discontinuation of the clamp.

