| N=6 | | | | MK-1092 SC (≤ 64 nmol/kg) |
| N=2 | | | | Glargine 3.0 nmol/kg SC |

SC – Subcutaneous; T1DM – Type 1 Diabetes Mellitus
 Subjects will only participate in one panel.
 The starting dose of MK-1092 in Panel G was 8.0 nmol/kg based on the results of Part 1. Doses for Panels H-J will be determined following review of the safety, tolerability, pharmacokinetic and/or pharmacodynamic data observed in previous panels and will not exceed a maximum dose of 64 nmol/kg.
 To maintain blinding, subjects will receive two injections at each administration – one active (MK-1092 or glargine) and one placebo due to potential differing volumes of the active treatments.
[†]Panel I will be omitted per PCL #10.

Table 6 Sample Allocation Schedule (Part 4)

| Subjects (T2DM) | Period 1 | Period 2 | Period 3 |
|-----------------|-------------------------|-------------------------|---------------------------------|
| N=6 | MK-1092 SC (32 nmol/kg) | MK-1092 SC (16 nmol/kg) | MK-1092 SC (≤ 64 nmol/kg) |
| N=3 | Glargine 3.0 nmol/kg SC | Glargine 3.0 nmol/kg SC | Glargine 3.0 nmol/kg SC |

SC – Subcutaneous; T2DM – Type 2 Diabetes Mellitus
 Subjects will participate in all periods. Subjects who receive MK-1092 in Period 1 will receive MK-1092 in subsequent periods, and subjects who receive glargine in Period 1 will receive glargine in subsequent periods.
 The starting dose of MK-1092 in Period 1 will be 32 nmol/kg based on the results of Part 1. Doses for Periods 2 and 3 will be determined following review of the safety, tolerability, pharmacokinetic and/or pharmacodynamic data observed in previous periods and will not exceed a maximum dose of 64 nmol/kg.
 To maintain blinding, subjects will receive two injections at each administration – one active (MK-1092 or glargine) and one placebo due to potential differing volumes of the active treatments.

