5.11 Clinical Criteria for Early Trial Termination

There are no pre-specified criteria for terminating the trial early.

A primary objective of this early Phase I trial is to identify the maximum safe and well-tolerated dose and/or dosing regimen that achieve pharmacokinetic, pharmacodynamic and/or biologic targets in humans based on preclinical or early clinical data. Therefore, it is possible that trial subjects may not receive all doses specified in the protocol if this objective is achieved at lesser dose levels in this trial. This would not be defined as early termination of the trial, but rather an earlier than anticipated achievement of the trial objective(s). If a finding (e.g., pharmacokinetic, pharmacodynamic, efficacy, biologic targets, etc.) from another preclinical or clinical trial using the trial treatment(s), comparator(s), drug(s) of the same class, or methodology(ies) used in this trial, results in the trial(s) or program being stopped for non-safety reasons, this also does not meet the definition of early trial termination.

Early trial termination is defined as a permanent discontinuation of the trial due to unanticipated concerns of safety to the trial subjects arising from clinical or preclinical trials with the trial treatment(s), comparator(s), drug(s) of the same class or methodology(ies) used in this trial.

| All Panels ^a | | | | | | | | | | | | | | | | | | | | | | | |
|---|------------------|------|----------|-------|-------|-----|-----|-----|-----|------|------|------|------|------|-------------------------|------|------|------|-------|-------|----|---|---|
| | Scr ^b | D -1 | D1 | | | | | | | | | | | D 2 | | | D3 | D4 | D5 | D6 | D8 | Post-trial (Day 14 +/- 2 days) ^t | Post-trial (Day 28 +/- 3 days) ^t |
| | | | Pre-dose | 0 | 1 h | 2 h | 4 h | 6 h | 9 h | 12 h | 18 h | 24 h | 30 h | 36 h | Post clamp ^p | 48 h | 72 h | 96 h | 120 h | 168 h | | | |
| Urine Drug Screen (UDS) ^j | X | X | | | | | | | | | | | | | | | | | | | | | |
| Breath Alcohol Assessment | X | X | | | | | | | | | | | | | | | | | | | | | |
| HIV/Hepatitis Screen (per site SOP) | X | | | | | | | | | | | | | | | | | | | | | | |
| Blood for Genetic Analysis ^k | | | X | | | | | | | | | | | | | | | | | | | | |
| Blood for Glucose Analysis ⁿ | X | | | | | | | | | | | | | | | | | | | | | | |
| Blood for Non-Esterified Fatty Acids (NEFA) | | | X | | X | X | | X | X | X | | X | | | | | | | | | | | |

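### Does comparing the therapeutic exposure target with AUC0-24 in one section and AUC0-∞ in the next leave it unclear whether a dose reached that target?

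*Combined protocol and SAP*

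**What the plan says.** Section 4.2.2.2 projects that 12.6 nmol/kg SC gives the target clamp response in healthy and T1DM subjects. That dose "is projected to lead to an exposure (AUC_{0-24hr} at steady state) of 29 nM*hr, assuming linear PK". The section adds: "A range of exposure around this predicted therapeutic dose was anticipated in Part 1 between Panels B (8.0 nmol/kg SC) and C (16 nmol/kg SC". It then turns to the observed AUC0-24, which "was 12.9 nM*h at 8.0 nmol/kg and 26.0 nM*h at 16 nmol/kg".

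Section 4.2.2.3 carries the target over to T2DM: "the therapeutic exposure level for insulin resistant subjects with T2DM is estimated to be 58 nM*h". It describes this as twice the healthy and T1DM value. It compares it with a projected AUC0-∞ of 146 nM*hr at 64 nmol/kg, stated as about 2.5 times the target.

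The PK table in section 4.1.2 gives both metrics for each dose, in the order Cmax, AUC0-∞, AUC0-24, as geometric mean (CV). The 16 nmol/kg row reads "1.63 (12.68) | 37.8 (10.09) | 26.03 (21.43" and the 32 nmol/kg row reads "2.91 (18.73) | 75.8 (10.28) | 48.86 (15.83". PK from Panel H and from Part 4 was pending.

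On later dosing, the notes to Table 6 in section 5.3 say: "Doses for Periods 2 and 3 will be determined following review of the safety, tolerability, pharmacokinetic and/or pharmacodynamic data observed in previous periods". Section 5.11 says that "trial subjects may not receive all doses specified in the protocol if this objective is achieved at lesser dose levels".

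**The concern.** The 29 nM*hr target is a steady-state quantity, while the values printed after it come from a single dose truncated at 24 hours. Median Tmax is 12 to 18 hours, so a sizeable part of a single-dose profile falls after 24 hours. A reader who takes the figures at face value sees 12.9 and 26.0 against 29 and concludes that neither panel reached the predicted exposure. Section 4.2.2.3 then uses AUC0-∞ without restating the metric of its 58 nM*h target.

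If the two metrics were interchangeable, it would be unclear whether 32 nmol/kg, the Part 4 Period 1 dose, reached the T2DM target. PK is among the data reviewed before later Part 4 doses, and planned doses may be dropped once targets are met. An ambiguous target could therefore affect how the pending PK is read.

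**Working it through.** **1. Reproduce the plan's projections.** Section 4.2.2.2 projects 9.1 nM*hr at 4.0 nmol/kg with F = 0.4.

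- Slope: 9.1 / 4.0 = 2.275 nM*hr per nmol/kg
- 12.6 × 2.275 = 28.7 (stated 29)
- 2 × 29 = 58 (stated 58)
- 64 × 2.275 = 145.6 (stated 146); 146 / 58 = 2.52 (stated about 2.5)
- 64 × 2.275 / 0.4 = 364 at F = 1 (stated 366)
- Margins to the dog exposure of 479: 479 / 9.1 = 52.6, 479 / 29 = 16.5, 479 / 146 = 3.28, 479 / 366 = 1.31 (stated about 52, 16, 3.3 and 1.3)

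One slope yields both the steady-state AUC0-24 of 29 and the AUC0-∞ of 146. That is expected: with linear, time-invariant PK and once-daily dosing, AUC over a steady-state dosing interval equals single-dose AUC0-∞. Section 4.2.2.2 also checks its 9.1 projection against an observed 9.86, which is the AUC0-∞ entry for 4.0 nmol/kg in section 4.1.2 (the AUC0-24 entry is 6.43).

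**2. Set the observed values beside the targets** (section 4.1.2; ratio = AUC0-24 / AUC0-∞).

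| Part, dose (nmol/kg) | AUC0-∞ | AUC0-24 | Ratio |
|---|---|---|---|
| Part 1, 4.0 | 9.86 | 6.43 | 0.65 |
| Part 1, 8.0 | 17.8 | 12.94 | 0.73 |
| Part 1, 16 | 37.8 | 26.03 | 0.69 |
| Part 1, 32 | 75.8 | 48.86 | 0.64 |
| Part 1, 64 | 161 | 108 | 0.67 |
| Part 3, 8.0 | 22.6 | 13.9 | 0.62 |

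Single-dose AUC0-24 omits 27% to 38% of AUC0-∞. In Part 1 only 16 nmol/kg changes side of 29 (26.03 or 37.8), and only 32 nmol/kg changes side of 58 (48.86 or 75.8).

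**3. Which metric fits the plan's own doses?** Linear interpolation between adjacent Part 1 doses gives:

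- 29 on AUC0-∞: 8 + 8 × (29 − 17.8) / (37.8 − 17.8) = 12.5
- 58 on AUC0-∞: 16 + 16 × (58 − 37.8) / (75.8 − 37.8) = 24.5
- 29 on AUC0-24: 16 + 16 × (29 − 26.03) / (48.86 − 26.03) = 18.1
- 58 on AUC0-24: 32 + 32 × (58 − 48.86) / (108 − 48.86) = 36.9

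The plan states 12.6 and about 25. AUC0-∞ recovers both and AUC0-24 recovers neither.

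**4. Precision at 32 nmol/kg.** The 95% interval is GM × exp(± t(5) × √ln(1 + CV²) / √6), taking the planned n = 6 and treating the tabulated CV as geometric; both are assumptions. AUC0-24 gives 41.4 to 57.6 and AUC0-∞ gives 68.1 to 84.4. With n = 5 they are 40.2 to 59.4 and 66.7 to 86.1. The AUC0-24 interval then includes 58, while the AUC0-∞ interval stays above it.

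**5. What depends on the targets?**

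- Section 4.2.2.4 bases the Period 1 dose on safety and tolerability in Part 1, and later Part 4 decisions primarily on safety and tolerability in earlier periods.
- Section 4.1.2 says the Period 2 dose was chosen to explore PD effects below 32 nmol/kg.
- Section 5.2.1.2 permits PK and PD data in escalation decisions but names no exposure threshold.
- Section 4.2.2.3 lists the grounds for withholding 64 nmol/kg as PD targets reached, safety findings, or an unsatisfactory exposure margin. The 58 figure is not one of them.
- In section 8 the primary PD hypothesis concerns mean GIRmax between 1.5 and 4.5 mg/kg/min in T1DM. No analysis uses 29 or 58.
- The exposure targets stand in for a GIR of about 1 to 2 mg/kg/min. Section 4.1.2 already reports GIRmax measured in T2DM: 1.4 at 16 nmol/kg and 1.9 at 32 nmol/kg.

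**The case for a change.** The best case for an edit is that section 4.2.2.2 changes metric between consecutive paragraphs and prints the column that does not match its own definition. PK is a named input to the remaining dose decisions, and section 5.11 includes pharmacokinetic targets among those whose achievement may end dosing early. Someone reading the pending Panel H and Part 4 PK might take AUC0-24 as the yardstick. The remedy would be a sentence drawn from a table already in the protocol.

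The first point stands: 17.8 and 37.8 are the like-for-like figures, and the text does not say so. The consequences do not follow.

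- The protocol nowhere compares 32 nmol/kg, or the 58 target, with AUC0-24. Section 4.2.2.2 gives correctly labelled values for two other doses and draws no conclusion from them. It says that the predicted dose was expected to lie between Panels B and C, and 12.6 lies between 8 and 16 on any metric.
- The 58 target is twice a quantity whose metric is defined, so the metric carries over.
- Panels H and J enrol T1DM subjects, for whom the target is 29. At 32 nmol/kg both Part 1 values, 48.86 and 75.8, exceed it.
- Showing the observed 161 beside the predicted 146 at 64 nmol/kg would change the multiple of 58 from about 2.5 to 161 / 58 = 2.8, and the margin from about 3.3 to 479 / 161 = 3.0. Section 4.1.2 already reports 161, and the adequacy of the margin is not in question.

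**Conclusion.** The mismatch is confined to one sentence of background rationale in section 4.2.2.2. Read literally, it understates exposure relative to the target by 27% at 8.0 nmol/kg and 31% at 16 nmol/kg (ratios 0.73 and 0.69). Section 4.2.2.3 is consistent with the definition, and the documents give one answer on the defined metric: 16 nmol/kg exceeds 29 (37.8) and 32 nmol/kg exceeds 58 (75.8). A pharmacokineticist reading the pending data would make this conversion as a matter of course, and both metrics are tabulated side by side.

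No endpoint, analysis, stated dosing rule or safety margin depends on the choice, so changing the sentence would not alter what the trial does or concludes. The plan can stand.

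This rests on linear, time-invariant PK with once-daily dosing. Linearity is the protocol's own assumption, and section 4.1.2 reports approximate dose proportionality. The comparison with 58 uses healthy-subject PK, because the T2DM results were pending. It implies nothing about which dose should be given.
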